###### Baseline Conditions

Any pre-existing medical conditions considered as relevant by the investigator, excluding the indication of the trial, are recorded into the eCRF in the appropriate page.

Any abnormal clinical significant findings observed during ophthalmological examinations at Visit 1 need to be documented as Baseline Conditions.

Medical History:

All relevant medical history according to the investigator judgment will be captured in the eCRF.

Re-screening:

Patients who do not fulfil all eligibility criteria for a reason that later resolves and allows eligibility criteria to be met within a 12-week period after the initial screening visit, can be re-screened up to one time. For re-screening a new patient number will be assigned, and the patient must sign a new Informed Consent Form (ICF). Imaging of retina (SD-OCT, fundus photography) does not need to be repeated at the re-screening visit if the corresponding criteria for inclusion of the study eye were met at the initial screening visit and the images are not older than 28 days at the re-screening visit; otherwise new images have to be performed.

6.2.1.2 Treatment period(s) of SRD part

IVT injections must be carried out according to medical standards and applicable guidelines by a qualified physician experienced in administering IVT injections and will be done as part of Visit 2 procedures after the ophthalmological assessments in [Flow Chart I](#) have been performed (please see [Section 4.1.4](#) for details). After administration of BI 754132, patients will be monitored according to standard practice and at least for 1 hour. In this minimum post-dose observation period, systemic and ocular conditions will be monitored according to local practice for such procedures. An additional tonometry could be performed after IVT injection to monitor IOP.

6.2.1.3 Follow-up period and trial completion of SRD part

Patients must continue to be followed according to the visit schedule (unless they withdraw consent for further follow-up) in order to collect data up to the end of the planned observation period. Unscheduled visits will be possible at the discretion of the investigator at any time for safety reason. The unscheduled visits may include any assessments considered necessary by the investigator. All unscheduled visits should be described and documented in the medical /source record. The investigator may decide to administer standard treatment for ocular inflammation during the follow-up period as deemed medically appropriate.

Visit 10/End of Trial:

The Visit 10/EOT will be performed 16 days after the Visit 9 (see [Flow Chart I](#)).

The Visit 10/EOT is the final visit and the trial completion page in the eCRF has to be entered.

Withdrawal of consent

If a patient is not willing to continue in the trial and wants to withdraw consent prior to the end of the trial, Visit 9 should be scheduled as soon as possible, and also Visit 10/EOT should be performed to assess for safety and if patient agrees.

If patient refuses to participate at a Visit 9 or Visit 10, the trial completion page of the eCRF has to be filled in.

## 6.2.2     Multiple Dosing Part

### 6.2.2.1    Screening and run-in period(s) of MD part

#### Screening Period

The screening visit does not need to be done with the patient in a fasted state.

All patients must sign an Informed Consent consistent with ICH GCP guidelines prior to any study specific procedures, this includes the option that the patient signs the Informed Consent during an extra contact to the study site prior to the actual screening visit. The patient should be recorded on the enrolment log as a screened patient when Visit 1 is performed.

Visit 1 is the beginning of the screening period. As soon as eligibility of enrolled patients is confirmed, the treatment visit (Visit 2) may be performed.

If the screening visit has been performed earlier than 14 days before the dosing visit, an additional visit for repeating of safety lab, vital signs, ECG and targeted physical examination has to be performed again.

#### Baseline Conditions

Any pre-existing medical conditions considered as relevant by the investigator, excluding the indication of the trial, are recorded into the eCRF in the appropriate page.

Any abnormal clinically significant findings observed during ophthalmological examinations at Visit 1 need to be documented as Baseline Conditions.

#### Medical History:

All relevant medical history according to the investigator judgment will be captured in the eCRF.

#### Re-screening:

Patients who do not fulfil all eligibility criteria for a reason that later resolves and allows eligibility criteria to be met within a 12-week period after the initial screening visit, can be re-screened up to one time. For re-screening, a new patient number will be assigned, and the patient must sign a new ICF. Imaging of retina (SD-OCT, fundus photography) does not need to be repeated at the re-screening visit if the corresponding criteria for inclusion of the study eye were met at the initial screening visit and the images are not older than 28 days at the re-screening visit; otherwise new images have to be performed.

### 6.2.2.2    Treatment period(s) of MD part

IVT injections must be carried out according to medical standards and applicable guidelines by a qualified physician experienced in administering IVT injections and will be done as part of Visit 2, Visit 3 and Visit 4 procedures after the ophthalmological assessments in [Flow Chart II](#) have been performed (please see [Section 4.1.4](#) for details).

Post-injection assessments:

After study drug administration a gross visual function test (e.g. finger counting/hand motion) will be performed within 15 minutes. IOP will be measured between 30-50 minutes after the injection. Patients will be monitored according to standard practice and at least for 1 hour. In this minimum post-dose observation period, systemic and ocular conditions will be monitored and treated according to local practice for such procedures.

**6.2.2.3 Follow-up period and trial completion of MD part**

Patients must continue to be followed according to the visit schedule (unless they withdraw consent for further follow-up) in order to collect data up to the end of the planned observation period. Unscheduled visits will be possible at the discretion of the investigator at any time for safety reason. The unscheduled visits may include any assessments considered necessary by the investigator. All unscheduled visits should be described and documented in the medical/source record. The investigator may decide to administer standard treatment for ocular inflammation during the follow-up period as deemed medically appropriate.

Visit 7/End of Trial:

The Visit 7/EOT will be performed 42 days after the Visit 6 (see [Flow Chart II](#)).

The Visit 7/EOT is the final visit and the trial completion page in the eCRF has to be entered.

Withdrawal of consent

If a patient is not willing to continue in the trial and wants to withdraw consent prior to the end of the trial, the investigator should offer the possibility to continue the trial without further treatment until Visit7/EOT. If patient disagrees to continue under these circumstances, Visit 6 should be scheduled as soon as possible, and also Visit 7/EOT should be performed to assess for safety.

If patient refuses to participate at a Visit 6 or Visit 7, the trial completion page of the eCRF has to be filled in.

## 7. STATISTICAL METHODS AND DETERMINATION OF SAMPLE SIZE

The main objective of this trial is to investigate ocular and systemic safety and tolerability as well as pharmacokinetics of single intravitreal and multiple intravitreal administrations of BI 754132. This will be assessed by calculating descriptive statistics for safety and PK parameters, which will be compared between the treatment groups.

### 7.1 NULL AND ALTERNATIVE HYPOTHESES

No confirmatory testing is performed and hence no null and alternative hypotheses are defined. A discussion of the sample size is provided in [Section 7.5](#).

### 7.2 PLANNED ANALYSES

#### 7.2.1 General considerations

##### 7.2.1.1 Dose escalation in the SRD part

The dose escalation will be guided by a Bayesian 2-parameter logistic regression model with overdose control [[R13-4803](#), [R13-4806](#)]. For a given dose, the EWOC criterion is that there should be less than 25% risk that the true ocular and systemic DLE rate is above 0.25. The BLRM will not be used for the analysis of the primary endpoint.

The model is given as follows:

$$\text{logit}(\pi_d) = \log(\alpha) + \beta * \log(d/d^*),$$

where  $\text{logit}(\pi) = \log(\pi/(1-\pi))$ ,  $\pi_d$  represents the probability of having a DLE in the evaluation period at dose  $d$ ,  $d^* = 6$  mg is the reference dose, allowing for the interpretation of  $\alpha$  as the odds of a DLE at dose  $d^*$ , and  $\theta = (\log(\alpha), \log(\beta))$  with  $\alpha, \beta > 0$  is the parameter vector of the model.

The estimated probability of a DLE at each dose level from the model will be summarized using the following intervals:

Target toxicity: [0.00, 0.25]

Over toxicity: [0.25, 1.00]

The BLRM-recommended dose for the next cohort is the dose level with the highest posterior probability of the DLE rate falling in the target interval [0.00, 0.25] among the doses fulfilling EWOC. Thus, it should be unlikely (< 25% posterior probability) that the DLE rate at that dose will exceed 0.25. However, the maximum allowable dose increment for the subsequent cohort will be no more than 233% from the previous dose up to doses of 3 mg, and to a maximum of 100% from the previous dose from dose 3 mg onwards. Dose escalation will continue up to the 6 mg dose as long as the EWOC criterion for the next dose level is fulfilled. At the final dose, at least 6 treated patients are required. However, the SMC may decide to include an additional number of patients at this dose level.

Since a Bayesian approach is applied, a prior distribution  $f(\theta)$  for the unknown parameter vector  $\theta$  needs to be specified. This prior distribution will be specified as a mixture of three multivariate normal distributions, i.e.

$$f(\theta) = a_1 f_1(\theta) + a_2 f_2(\theta) + a_3 f_3(\theta)$$

with  $a_i$ ,  $i = 1, 2, 3$  the prior mixture weights ( $a_1 + a_2 + a_3 = 1$ ), and  $f_i(\theta) = \text{MVN}(\mu_i, \Sigma_i)$ , the multivariate normal distribution of the  $i$ -th component with mean vector  $\mu_i$  and covariance matrix  $\Sigma_i$ , where

$$\Sigma_i = \begin{pmatrix} \sigma_{i,11}^2 & \sigma_{i,11}\sigma_{i,22}\rho_i \\ \sigma_{i,11}\sigma_{i,22}\rho_i & \sigma_{i,22}^2 \end{pmatrix}.$$

Mixture prior distributions have the advantage that they allow for specification of different logistic dose-toxicity curves, therefore making the prior more robust.

For the current study, no relevant information in the form of human data was available, since no study in a comparable population has been conducted. Therefore, the three mixture components were established as follows:

1. A weakly informative prior was derived reflecting the a priori assumption that the median DLE rate at the starting dose of 0.3 mg would equal 0.01, and the median DLE rate at the maximum feasible dose of 6 mg would equal 0.10. This yields  $\mu_1 = (-2.197, -0.223)$ . The standard deviations were set such that large uncertainty about the parameter means is reflected, and the correlation was set to 0, thus yielding  $\sigma_{1,11} = 2$ ,  $\sigma_{1,22} = 1$  and  $\rho_1 = 0$ , respectively. The prior weight  $a_1$  for the first component was chosen as 0.9.
2. A high-toxicity weakly informative prior was derived reflecting the case that the compound would be much more toxic than expected. For this prior component, it was assumed that the median DLE rate at the starting dose of 0.3 mg would equal 0.10, and the median DLE rate at 6 mg would equal 0.40. These assumptions yield  $\mu_2 = (-0.405, -0.514)$ . The standard deviations and correlations were set identical to the weakly informative prior, i.e.  $\sigma_{2,11} = 2$ ,  $\sigma_{2,22} = 1$  and  $\rho_2 = 0$ , respectively. The prior weight  $a_2$  for the second component was chosen as 0.05.
3. A low-toxicity weakly informative prior was derived reflecting the case that the compound would be much less toxic than expected. For this prior component, it was assumed that the median DLE rate at the starting dose of 0.3 mg would equal 0.001, and the median DLE at 6 mg would equal 0.01. These assumptions yield  $\mu_3 = (-4.595, -0.259)$ . The standard deviations and correlations were set to  $\sigma_{3,11} = 5$ ,  $\sigma_{3,22} = 0.01$ , therefore almost fixing the slope parameter to its mean. The correlation was set to 0, i.e.  $\rho_3 = 0$ . The prior weight  $a_3$  for the third component was chosen as 0.05.

A summary of the prior distribution is provided in [Table 7.2.1.1: 1](#). Additionally, the prior probabilities of DLEs at different doses, as well as the corresponding probability of targeted and overdosing, are shown in [Table 7.2.1.1: 2](#). Graphically, the prior medians with accompanying 95% credible intervals are shown in [Figure 7.2.1.1: 1](#). As can be seen from both [Table 7.2.1.1: 2](#) and [Figure 7.2.1.1: 1](#), the prior medians of the DLE probabilities are in line with the prior medians derived from the weakly informative prior, and the uncertainty around the medians is large, showing the low amount of information this prior provides. This

is also supported by the prior sample size, i.e. the information contained in the prior. This is approximately equal to 1.7 patients. A detailed evaluation of the model using hypothetical data scenarios and operating characteristics is provided in [Appendix 10.4](#).

Table 7.2.1.1: 1 Summary of prior distribution

Prior Component	Mixture Weight	Mean Vector	SD Vector
1: Weakly inf.	0.900	-2.197 -0.223	2.00 1.00
2: High Tox.	0.050	-0.405 -0.514	2.00 1.00
3: Low Tox.	0.050	-4.595 -0.259	5.00 0.01

Table 7.2.1.1: 2 Prior probabilities of DLEs at selected doses

Dose	Probability of true DLE rate in		Mean	SD	Quantiles		
	[0, 0.25)	[0.25, 1]			2.5%	50%	97.5%
0.3	0.917	0.083	0.067	0.151	0.000	0.007	0.599
1	0.876	0.124	0.096	0.179	0.000	0.017	0.704
3	0.799	0.201	0.147	0.214	0.000	0.048	0.810
6	0.696	0.304	0.212	0.249	0.001	0.101	0.882

Median (95% CrI)

[figure not shown]

Figure 7.2.1.1: 1 Prior medians and 95% credible intervals

The prior may be updated once the trial has started in case new data that can be used will be available. Only patients for which the occurrence of DLEs within the evaluation period can be evaluated will be considered. The prior that is used for each BLRM analysis for the SMC meetings will be documented in the SMC minutes, the prior used for the final analysis will be documented in the TSAP.

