### 3. DESCRIPTION OF DESIGN AND TRIAL POPULATION

#### 3.1 OVERALL TRIAL DESIGN AND PLAN

The trial will consist of an SRD part followed by an MD part. Both parts will be conducted in a non-randomized, open-label, and uncontrolled manner.

SRD part:

Cohorts of patients will receive escalating doses of BI 754132, with the starting dose 0.3 mg. The other provisional dose levels are 1 mg, 3 mg, and the maximum planned dose 6 mg. Each cohort will consist of 3 newly enrolled patients. For each cohort, a single patient will be dosed on day 1, and the dosing investigator, coordinating investigator and 2 representatives of the sponsor who are involved in the trial will carefully evaluate all being available systemic (i.e. physical examinations, safety lab parameters, ECG and AEs) and ophthalmological (i.e. as defined in [Section 5.2.1](#)) safety data until day 4. If this patient neither has experienced an ophthalmological nor a systemic DLE, the remaining 2 patients will be dosed. Written minutes of this assessment are being distributed to all investigators participating in this trial part.

A Safety Monitoring Committee (SMC, see [Section 8.7](#)) will decide on the next dose level to be investigated, the size of the next cohort based on occurrence of DLEs and on additional information (systemic PK and patient profiles). Refer to [Figure 3.1.1](#) for a schematic representation of the dose escalation.

A Bayesian logistic regression model (BLRM) based on a weakly informative prior distribution, and employing the escalation with overdose control (EWOC) principle will be used for guiding the dose escalation (see [Section 7.2.1.1](#)). After all patients in a cohort have either experienced a DLE or have been observed for at least the 7 days evaluation period without experiencing a DLE (i.e. 7 days after drug administration, until Visit 4, will be evaluated per patient), the BLM will be updated with the newly accumulated data. The BLM provides estimates for the probability of observing a DLE for each planned dose. Dose escalation will be permitted to the next planned dose which fulfils the EWOC criterion. Note that this may also result in repeating the current dose level, or in going down to a lower dose level again.

For any dose-escalation cohort, at least 3 evaluable patients will be required.

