If DLEs are observed in the first two consecutive patients of a previously untested dose level, subsequent enrolment to that cohort will be stopped. The BLM will be re-run to confirm that the dose level still fulfils the EWOC principle. Based on this information, the SMC will evaluate whether the next patients will be enrolled at the same dose level, or if they will be enrolled at a lower dose level.

As a sensitivity analysis, the BLM might also be run again shortly before the SMC meeting, using all AE data available up to this time point.

The maximum tolerated dose (MTD) is considered as reached if at least 6 patients have been evaluated at a dose level which is the model's recommendation for the next dose cohort. Note that the MTD will likely be the highest feasible dose, 6 mg, rather than the highest tolerable dose in a strict sense. The SMC may decide on stopping the dose escalation after the criterion for MTD is fulfilled. Further patients may be included to confirm that the EWOC criterion is still fulfilled.

In [Figure 3.1: 1](#), the dose escalation process is depicted as planned, i.e., if no DLE occurs in the trial and dose escalation may proceed up to the highest dose level.

[figure not shown]

Figure 3.1: 1 Schematic representation of the dose escalation process in the SRD part

MD part:

The MD part will consist of one dose cohort (6 patients). After the SRD part has been completed, the SMC will decide on the selection of the highest dose (e.g. 6 mg) established as safe and tolerable during the SRD part to be used in the MD part. Patients that had received a dose in the SRD part of the trial (regardless of the eye) will not be included. In the MD part, patients will receive three consecutive dose injections over a 3-month period (dosing every 4 weeks).

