The measurement of the ERG a-wave in the STZ rat model represents a reliable animal surrogate to evaluate the effect of TrkB activation on photoreceptor function supporting the therapeutic benefit in GA patients. In an-in-house study using such a model [n00254511-01] the targeted efficacious dose for BI 754132 was calculated to be a trough EC50 of 6.38 nM based on the pharmacological data of EX00077780 (tool TrkB antibody that cross reacts to the rat TrkB receptor). The human dose estimation of BI 754132 was performed based on scaling the PK/PD of the tool antibody from rat to human and comparison of PK between BI 754132 and Avastin [n00264883-01, R18-2968]. Taking into consideration the vitreous humor volume, the estimated human intravitreal half-life ( $t_{1/2} = 9.73$  days) and the Ctrough value, an injection of 3 mg/eye every 90 days would maintain intravitreal concentration above the required Ctrough of 6.38 nM.

The proposed starting dose of 0.3 mg/eye is predicted to maintain the predicted minimal efficacious vitreal concentration of 6.38 nM for 60 days. Doses lower than 0.3 mg are also expected to induce PD effects in the eye, however the duration of the effect would be smaller and in the light to slow down/halt GA progression with special emphasis on photoreceptor degeneration this PD effect would not be long enough to justify a potential long term benefit to the patients.

For the 1 mg and 3 mg dose, the relative increase to the next dose is 233% and 200%, respectively. These doses limit the dose steps and resulting number of trial related IVT injections. Before each subsequent dose is administered, an external safety monitoring committee will be convened to determine if it is safe to proceed to the next dose. If all previous doses are clinically well tolerated, one additional dose of 6.0 mg will be tested, as one of the development objectives is to find a dose that provides extended drug exposure and therefore longer efficacy and less injection frequency.

The provisional dose levels to be assigned to separate cohorts of patients are listed in Table 4.1.2: 1. Intermediate or lower dose levels, depending on the number of DLEs observed in the study, as long as they fulfil the EWOC criterion, may be investigated if agreed upon between Investigator and Sponsor.

Table 4.1.2: 1      Provisional dose levels for escalation

Dose level	Proposed dose	Relative increment from previous dose
1	0.3 mg	Starting dose

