#### 7.2.1.2 Subject analysis sets

The main analysis populations are defined below. In the TSAP, further analysis data sets may be defined. Patients will be analysed according to the assigned treatment, unless otherwise specified. Patients who are replaced during the DLE evaluation period will be excluded from the determination of the MTD (see [Section 3.1](#)).

Important protocol deviations (iPDs) will be defined in the Integrated Quality and Risk Management (IQRM) plan. IPDs will be identified no later than in the Report Planning Meeting, and the iPD categories will be updated as needed. The handling of patients with iPDs will be described in the TSAP.

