### 8.1 TRIAL APPROVAL, PATIENT INFORMATION, INFORMED CONSENT

This trial will be initiated only after all required legal documentation has been reviewed and approved by the respective Institutional Review Board (IRB / Independent Ethics Committee (IEC and competent authority (CA) according to national and international regulations. The same applies for the implementation of changes introduced by amendments.

Prior to patient participation in the trial, written informed consent must be obtained from each patient (or the patient's legally accepted representative) according to ICH-GCP and to the regulatory and legal requirements of the participating country. Each signature must be personally dated by each signatory and the informed consent and any additional patient-information form retained by the investigator as part of the trial records. A signed copy of the informed consent and any additional patient information must be given to each patient or the patient's legally accepted representative.”

The investigator or delegate must give a full explanation to trial patients based on the patient information form. A language understandable to the patient should be chosen, technical terms and expressions avoided, if possible.

The patient must be given sufficient time to consider participation in the trial. The investigator or delegate obtains written consent of the patient's own free will with the informed consent form after confirming that the patient understands the contents. The investigator or his delegate must sign (or place a seal on) and date the informed consent form. If a trial collaborator has given a supplementary explanation, the trial collaborator also signs (or places a seal on) and dates the informed consent:

Re-consenting may become necessary when new relevant information becomes available and should be conducted according to the sponsor's instructions.

The consent and re-consenting process should be properly documented in the source documentation.

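### The Section 7.2.1.1 definition of the BLRM-recommended dose always selects the lowest available dose, or none, and the MTD criterion depends on it

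*Protocol*

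**What the plan says.** Protocol Section 7.2.1.1 sets two intervals for the DLE rate: target, 0 to 0.25, and overdose, 0.25 to 1. A dose meets EWOC if the posterior probability of a DLE rate above 0.25 is below 25%. The section then defines the recommendation: "The BLRM-recommended dose for the next cohort is the dose level with the highest posterior probability of the DLE rate falling in the target interval", taken over the doses that meet EWOC.

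Four other places describe a different rule.

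- The same paragraph: "Dose escalation will continue up to the 6 mg dose as long as the EWOC criterion for the next dose level is fulfilled".
- Section 3.1: "Dose escalation will be permitted to the next planned dose which fulfils the EWOC criterion".
- Appendix 10.4, operating characteristics: the simulated trials moved to the largest dose that passed the overdose criterion and was at most a 234% increase.
- Table 10.4: 1: next doses of 1, 3 and 6 mg as DLE-free data build up.

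The increment limit in Section 7.2.1.1 "will be no more than 233% from the previous dose up to doses of 3 mg", and 100% from 3 mg onwards.

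Section 3.1 regards the MTD as reached when "at least 6 patients have been evaluated at a dose level which is the" model's recommendation for the next cohort. Section 7.2.1.2 points back to this: "Patients who are replaced during the DLE evaluation period will be excluded from the determination of the MTD". Section 4.1.2 leaves room for unplanned doses: "Intermediate or lower dose levels, depending on the number of DLEs observed in the study", provided they meet EWOC.

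SAP Section 7.4 promises the results of a final BLRM after the SRD part. The changes listed in SAP Section 4 do not touch the recommendation rule.

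**The concern.** Choosing the dose with the highest probability of lying in a target interval makes sense when there is also an under-dosing interval below it, because low doses then lose probability to that interval. Here there is none. Target and overdose are complements, so maximising the target probability is the same as minimising the overdose probability, and the safest dose always wins.

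This is the protocol's definition of the term BLRM-recommended dose, and the MTD criterion relies on the model's recommendation. Taken literally, among the planned doses only 0.3 mg could ever become the MTD. At stake is whether a recommended dose or MTD reported from the final BLRM would follow the rule the sponsor tabulated and simulated, or the one written in Section 7.2.1.1.

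**Working it through.** **Analytic step.** The model in Section 7.2.1.1 is logit(π_d) = log α + β·log(d/6), with β > 0. For every (α, β), π_d increases with d. Hence P(π_d ≥ 0.25 | data) increases with d, and P(target) = 1 − P(overdose) decreases with d, for any data and any prior. The EWOC dose with the highest P(target) is the lowest dose on offer. If that dose fails EWOC, every higher dose fails too and no dose is recommended.

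**Inputs for the numerical check.** The prior is the three-component mixture in Table 7.2.1.1: 1, with correlations zero:

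- weight 0.90, means (−2.197, −0.223), SDs (2, 1)
- weight 0.05, means (−0.405, −0.514), SDs (2, 1)
- weight 0.05, means (−4.595, −0.259), SDs (5, 0.01)

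The likelihood is binomial at each dose, and the posterior was obtained by grid integration.

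**Reproducing the plan's figures.** Prior P(overdose) at 0.3/1/3/6 mg comes to 0.082/0.124/0.201/0.306, against 0.083/0.124/0.201/0.304 in Table 7.2.1.1: 2. All P(overdose) values in Table 10.4: 1 are reproduced to within 0.012. Examples: scenario 3b 0.012 (table 0.013), scenario 7 0.256 (0.253), scenario 9 0.367 (0.364).

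**P(target) by dose, and the dose each rule names.**

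| Data | 0.3 mg | 1 mg | 3 mg | 6 mg | Section 7.2.1.1 | Table 10.4: 1 |
|---|---|---|---|---|---|---|
| Scenario 1: 0/3 at 0.3 mg | 0.983 | 0.956 | 0.883 | 0.770 | 0.3 mg | 1 mg |
| Scenario 5b: 0/6 at 0.3 mg, 2/6 at 1 mg | 0.954 | 0.776 | 0.444 | 0.304 | 0.3 mg | 1 mg |
| Scenario 3b: no DLE in 3/3/3/6 | 1.000 | 0.9999 | 0.999 | 0.988 | 0.3 mg | 6 mg |

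The conflict also shows in the protocol's printed figures alone. In scenario 1, 0.3 mg has P(overdose) 0.015, so P(target) is 1 − 0.015 = 0.985, yet the table recommends 1 mg with 0.960.

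**Agreement with the 16 scenarios, using the last cohort's dose as the previous dose.**

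| Rule | Scenarios matched |
|---|---|
| Section 7.2.1.1 as written | 2 (scenario 5 at 0.3 mg; scenario 2 with no dose) |
| Highest EWOC dose, cap of exactly 233% | 14 (misses 1 and 5b) |
| Highest EWOC dose, 234% below 3 mg and 100% from 3 mg | 16 |

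Fifteen rows of the table name a dose, and the written rule contradicts 14 of them.

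**The cap.** The planned step from 0.3 to 1 mg is (1 − 0.3)/0.3 = 233.3%. A 233% limit gives 0.3 × 3.33 = 0.999 mg, just short of 1 mg. This explains the two misses in the second row.

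**MTD criterion with no DLEs, cohorts of 3.** The written rule stays at 0.3 mg and meets the criterion there after 6 patients, when P(overdose) at 1 mg is only 0.022. The highest-EWOC-dose rule with the 234% cap goes 0.3, 1, 3, 6, 6 mg and meets it at 6 mg after 15 patients, in line with scenario 3b and Section 7.5.

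**A level below 0.3 mg.** As an illustration, suppose 0.1 mg (an assumed dose) were added after 0/3 at 0.3 mg. P(overdose) is 0.008 at 0.1 mg and 0.017 at 0.3 mg, so the written rule would choose 0.1 mg.

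**The case against.** The best defence is that nothing planned turns on this sentence. The SRD part has finished, with 3, 3, 3 and 6 patients at 0.3, 1, 3 and 6 mg and no DLE, so those running the trial evidently applied the intended rule. The SMC, not the model, chooses the dose. Section 7.2.1.1 says the BLRM is not used for the primary endpoint. The MD dose is the highest dose judged safe and tolerable, and SAP Table 6.1: 1 already gives it as 6 mg. Section 3.1 itself expects the MTD to be 6 mg. SAP Section 7.4 does not say that it will report a recommended dose or MTD. All of this stands, and it limits the consequence.

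It is also right that the completed data would not yield 0.3 mg as the MTD even on a literal reading. Only 3 patients were treated at that dose and the criterion needs 6, so no dose would qualify. That still differs from the 6 mg that the simulated rule gives.

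On the cap, 233% is plainly the rounded size of the planned step, and Table 4.1.2: 1 labels it so. This is a minor fault, worth mending only because the same paragraph needs correction and the simulations used 234%. The simulations also applied one 234% limit throughout, without the 100% cap from 3 mg. Among the planned doses this makes no difference, since 3 to 6 mg is exactly 100% and 6 mg is the top dose.

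None of these points makes the definition correct.

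**Conclusion.** The concern holds. The definition gives the wrong dose by construction; the result needs only β > 0 and a target interval that starts at zero, both stated in Section 7.2.1.1. The numerical results additionally assume the prior in Table 7.2.1.1: 1 and reproduce the plan's own figures closely.

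The operating characteristics in Appendix 10.4 are not undermined, because the appendix states the highest-dose rule for the simulations. The remaining exposure is conditional: a recommended dose or MTD given with the final BLRM would be wrong, or undefined, if taken from Section 7.2.1.1 as written. It should be fixed because it is a stated decision rule in a first-in-human protocol, the SAP leaves it uncorrected, and the repair is very small.

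**What to change.** Replace the sentence in Section 7.2.1.1 with: *The BLRM-recommended dose for the next cohort is the highest dose level fulfilling EWOC that is within the maximum increment (no more than 234% from the previous dose for previous doses below 3 mg, and no more than 100% from 3 mg onwards).* Change 233% to 234% in the increment limit of the same paragraph and in the Appendix 10.4 mention of the escalation rule. Refer to this definition in the MTD criterion of Section 3.1, and use it in SAP Section 7.4 or the report if a recommended dose or MTD is given.

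The protocol route is an amendment and needs the approvals in Section 8.1 ("The same applies for the implementation of changes introduced by amendments"), so it is worth doing only alongside another amendment. Otherwise, since the SRD part is complete, state the corrected definition as a change in SAP Section 4 and refer to it in SAP Section 7.4, one line in each. Neither route needs new data, patients or simulations.
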